## **5** ANALYSIS POPULATIONS

Per Amendment #5 of the protocol, the following analysis populations were defined for the study:

**Efficacy Population** – all patients who have received at least one dose of lucitanib and are confirmed as *FGFR1*-, 11q-amplified, or FGF non-amplified per the central laboratory.

Safety Population – all patients who have received at least one dose of lucitanib.

For the final statistical analyses to be conducted in support of the clinical study report, the **Efficacy Population** is redefined as all patients who have received at least one dose of lucitanib and have at least one post-baseline tumor scan.

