## **3** SAMPLE SIZE

Under the original protocol, approximately 160 patients were to be randomized 1:1 to the 10 mg and 15 mg daily dosing groups (Cohorts A and B).

Under protocol amendment 5, the following are the revised sample size considerations.

Up to 200 patients will be enrolled.

A total of at least 80 patients in the 10 mg arm is sufficient to reliably estimate the median PFS and 6 month PFS rate in these heavily pre-treated patients. An observed median PFS greater than 4 months or a 6-month PFS rate of at least 40% will be sufficient to consider the 10 mg dose group worthy of further study. Therefore, with at least 80 patients treated at 10 mg, the width of the 90% confidence interval for the 6 month PFS rate will be less than  $\pm 10\%$ , so that if the observed 6 month rate is 50% then the lower limit on the confidence interval will be greater than 40%.

The treatment effect in Cohort C (biomarker negative sub-group) is not expected to be as large as in Cohorts A and B; however, the same target of 40% will be used to evaluate Cohort C. With 40 patients, the width of the 90% confidence interval for the 6 month PFS rate will be less than  $\pm 15\%$ , so that if the observed 6 month rate is less than 25% then the upper limit on the confidence interval will be less than 40%, which is evidence that subsequent studies of 10 mg should exclude biomarker negative patients.

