## **4** GENERAL ANALYSIS CONSIDERATIONS

Due to significant changes to the study design throughout the study, all summaries of data will be presented by initial study drug dose level (10 mg, 15 mg) regardless of a patient's enrollment into study cohorts A, B, and C. Initial dose groups will be referred to as treatment groups (10 mg, 15 mg). An overall column combining all patients from both treatment groups will be included in the data summaries, where applicable.

Quantitative variables will be summarized using descriptive statistics (N, mean, standard deviation, median, minimum, and maximum) and/or frequency and percentages for medically relevant categories. Categorical variables will be presented using frequencies and percentages. Exact 95% confidence intervals may be presented for frequencies.

All data will be used to their maximum possible extent but without any imputations for missing data.

All statistical analyses will be conducted with the statistical analysis software (SAS®) System, Version 9.3 or higher.

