#### **6 PATIENT DISPOSITION**

The frequency and percentage of patients in each analysis population will be presented. The primary reason for discontinuation of lucitanib will be summarized.

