#### **8 DEMOGRAPHICS AND BASELINE CHARACTERISTICS**

Baseline characteristics and demographic data will be summarized for the safety population.

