## **12** EFFICACY ANALYSIS

#### **12.1** Primary Efficacy Analysis

Kaplan-Meier methodology will be used to summarize the time to event variables including the estimated 50th (median) percentile by treatment group.

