#### 12.1.1 Progression Free Survival (PFS)

PFS is defined as 1+ the number of days from the date of first dose of study drug to disease progression or death due to any cause, whichever occurs first. Patients without a documented event of progression will be censored on the date of their last adequate tumor assessment (i.e., radiologic assessment), or the date of randomization if no tumor assessments have been performed. Progression events will be determined by the investigator.

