## **17** SAFETY ANALYSIS

The safety analyses will be performed using the Safety Population.

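### SAP 5 restricts the Efficacy Population to scanned patients: if efficacy uses it, ORR and DCR rise when unscanned patients would be non-responders, while PFS and OS may shift either way

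*SAP*

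**What the plan says.** Protocol 11.1 defines the Efficacy Population by dosing and central confirmation of FGF status. It does not require a scan. SAP 5 repeats that definition and then, for the analyses that support the clinical study report, replaces it with "all patients who have received at least one dose of lucitanib and have at least one post-baseline tumor scan". Central FGF confirmation is dropped in the same sentence. The first on-treatment scan is due at C2D1 (Protocol 9.5.2.1).

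SAP 12 names no population for PFS, ORR, DCR or OS. The other population is assigned elsewhere: "Baseline characteristics and demographic data will be summarized for the safety population" (SAP 8) and "The safety analyses will be performed using the Safety Population" (SAP 17).

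SAP 12.1.1 measures PFS from first dose and counts death from any cause as an event. It sets no limit for deaths that follow missed assessments. For patients without an event it censors at the last adequate assessment, "or the date of randomization if no tumor assessments have been performed". Protocol 11.2.4.1 uses the date of first dose in that last case.

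The success rule is in SAP 3: "An observed median PFS greater than 4 months or a 6-month PFS rate of at least 40% will be sufficient" to regard 10 mg as worth further study. For PFS, SAP 12.1 itself names only "the estimated 50th (median) percentile by treatment group"; the 6-month rate comes from SAP 3 and Protocol 11.2.4.

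**The concern.** Having a post-baseline scan is an outcome of the first weeks on treatment, not a baseline feature. Patients without one include those who died early, deteriorated or stopped. A patient who dies on day 20 is a PFS event under SAP 12.1.1 but lies outside the redefined set. Patients never scanned also leave the denominators of ORR and DCR.

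The study has no concurrent control and is judged on observed absolute PFS, so no comparator absorbs a shift caused by the choice of set. The SAP also disagrees with itself. If unscanned patients are excluded, the censoring rule for patients without assessments has no use. If they are included, SAP 5 does not describe the set used for PFS.

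**Working it through.** **1. The plan's own figure.** SAP 3, n = 80, observed 6-month rate 50%: 1.645 × √(0.5 × 0.5 / 80) = 9.2 points, lower limit 40.8%. This agrees with the stated half-width below 10 points and lower limit above 40%. At the 40% bar the half-width is 1.645 × √(0.4 × 0.6 / 80) = 9.0 points.

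**2. Which set is used.** Two populations are defined. Safety is given to baseline and safety data, so the Efficacy Population has no evident use except efficacy. The rule in SAP 12.1.1 for patients without assessments points the other way. Steps 3 to 7 are conditional on the scanned set being used.

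**3. PFS, deaths before about C2D1 (day 29).** Let q be the share of treated patients who die before then, unscanned. The documents do not give q; 1%, 2.5% and 5% are assumptions. Once all patients are past the first scan, S_all(t) = (1 − q) × S_scanned(t).

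| q | True all-treated 40% appears as 0.40/(1 − q) | All-treated rate that appears as 40%: 0.40 × (1 − q) | Chance of meeting 40% bar if true rate is 38%, scanned set |
|---|---|---|---|
| 1% | 40.4% | 39.6% | 40.1% |
| 2.5% | 41.0% | 39.0% | 43.0% |
| 5% | 42.1% | 38.0% | 50.6% |

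The last column is exact binomial with n = 80 and complete 6-month follow-up: D ~ Bin(80, q), X ~ Bin(80 − D, 0.38/(1 − q)), P(X/(80 − D) ≥ 0.40). In all treated patients the chance is P(X ≥ 32) = 39.7%.

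Median limb: with 28-day cycles, C4D1 is day 85 (2.8 months) and C6D1 is day 141 (4.6 months), at 30.44 days per month. Four months lies between them. Ignoring deaths between scans and off-schedule scans, the limb is met when more than 50% are event-free after C4D1. In the scanned set that needs more than 0.50 × (1 − q) = 49.5%, 48.8% or 47.5% of all treated patients. The reported median will usually stay at the same scan, so no shift in months follows.

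**4. PFS, never-scanned patients who die later.** All patients are followed for survival (SAP 2.2.4) and SAP 12.1.1 counts any death. A never-scanned patient who dies at month 8 is therefore event-free at 6 months. Take 72 scanned patients, 30 of them event-free at 6 months: 30/72 = 41.7%.
- Add 4 unscanned deaths at day 20: 30/76 = 39.5% in all treated.
- Add instead 4 unscanned deaths at month 8: 34/76 = 44.7%.
- Add both groups: 34/80 = 42.5%.

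In general, with a unscanned deaths before 6 months and b after, the all-treated rate is (30 + b)/(72 + a + b). It exceeds 30/72 when b/(a + b) exceeds 30/72. Exclusion raises the reported rate only while fewer than that share of the dropped patients are event-free at 6 months.

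**5. PFS, living unscanned patients.** Censored at first dose, they leave the risk set before any event. Adding 4 of them to the first case in step 4 (80 treated) still gives 39.5%.

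**6. ORR and DCR.** With r responders, N treated and m unscanned non-responders, r/N becomes r/(N − m). Assumed ORR 16/80 = 20.0%: 16/76 = 21.1% (5% unscanned) and 16/72 = 22.2% (10%). Assumed DCR 40/80 = 50.0%: 40/76 = 52.6% and 40/72 = 55.6%.

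**7. OS.** Assume 72 scanned with 12-month OS of 40%, 4 deaths before a scan, and 4 unscanned survivors with 12-month OS u. All-treated OS = (72 × 0.40 + 4u)/80 = 37%, 39% or 41% for u = 0.2, 0.6 or 1.0, against 40% in the scanned set.

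**The case against.** The strongest objection is that the premise is inferred. SAP 12 does not say that efficacy uses the redefined set, SAP 12.1.1 provides for patients without assessments, and SAP 4 and 16.1 say data will be used as fully as possible. This stands as a limit. A reader might infer that the SAP plans no efficacy analysis of all treated patients, but for PFS the documents leave that open. It does not clear the plan, because SAP 5 and SAP 12.1.1 cannot both be right as written.

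A reader might also infer that the exclusion can only raise PFS and so makes the success rule easier to meet. Step 4 of the working shows otherwise: the inflation is confined to those who die early, and dropping never-scanned patients who die after 6 months lowers the reported rate.

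The effect is also likely to be small. Entry requires life expectancy above 6 months and ECOG 0 or 1 (Protocol 6.2), and the assumed shifts of 0.4 to 2.1 points are well inside the 9.0-point half-width. That is fair, though a confidence interval does not correct a bias.

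Finally, much could be recovered by hand. SAP 6 states that "The frequency and percentage of patients in each analysis population will be presented", which allows all-treated ORR and DCR to be worked out. Fatal adverse events are tabulated (SAP 17.1) and deaths within 28 days of the last dose are reported as serious adverse events (Protocol 10.2), so the effect of early deaths could be bounded. The exact all-treated PFS and OS curves could not be rebuilt. The redefinition is also stated openly, in a plan meant to precede final database lock (SAP 1).

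**Conclusion.** The point holds in conditional form and should be fixed. SAP 5 conditions the Efficacy Population on a post-treatment event, the structure of the SAP implies that efficacy uses it, and SAP 12.1.1 conflicts with it.

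If the set is used, ORR and DCR rise relative to all treated patients whenever the unscanned would count as non-responders, by about 1 to 2 points on an ORR of 20% with 5% to 10% unscanned (both assumed). Loss of deaths before about day 29 raises the 6-month PFS rate by 0.4 to 2.1 points at a true 40%, for assumed shares of 1% to 5%. Loss of never-scanned patients who die after 6 months acts in the opposite direction, so the net direction for PFS is not certain. The same is true of OS. The documents give neither the number unscanned nor the number of early deaths.

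All of this is relative to all treated patients. Against the protocol's own Efficacy Population the direction is unknown, because central FGF confirmation is dropped at the same time. Confidence is medium.

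**What to change.** - **SAP 5:** delete the post-baseline-scan requirement.
- **SAP 12:** state that PFS, OS, ORR and DCR are analysed in all treated patients, by the initial-dose groups of SAP 4. Count unscanned patients as non-responders for ORR and DCR, and deaths before the first scheduled scan as PFS events.
- **Deaths long after the last assessment, or with none:** state the rule, for example an event in the main analysis and censored in a sensitivity analysis.
- **SAP 12.1.1:** censor living unscanned patients at the date of first dose, as in Protocol 11.2.4.1. A randomization date does not exist for patients enrolled after Amendment #4.
- **Reporting:** give the number unscanned with reasons, and keep the scanned set as a labelled sensitivity analysis.

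The choice of FGF grouping is a separate matter.

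The cost is SAP wording and running the planned tables on a set that already exists, since all treated patients are the Safety Population. No new data are needed. ORR and DCR would become slightly less favourable; PFS may move slightly either way.

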#### **6 PATIENT DISPOSITION**

The frequency and percentage of patients in each analysis population will be presented. The primary reason for discontinuation of lucitanib will be summarized.

## 7 INCLUSION / EXCLUSION VIOLATIONS

The number of patients that violate each inclusion or exclusion criteria will be listed.

#### **8 DEMOGRAPHICS AND BASELINE CHARACTERISTICS**

Baseline characteristics and demographic data will be summarized for the safety population.

#### 8.1 Demographics

The demographic variables will be summarized with frequency tabulations. Descriptive statistics may also be used to summarize age, height, and weight. The categorical variables presented will include age, weight, sex, race, and ethnicity. Variable categorizations will be as follows:

- Age (years):  $\leq 40, 41-60, 61-80, > 80;$
- Weight (kg):  $\leq 50$ , > 50-75, > 75-100, > 100-125, > 125-150, > 150;
- Sex: Male, Female
- Race: American Indian or Alaska Native, Asian, Black, Native Hawaiian or Other Pacific Islander, White, Other
- Ethnicity: Hispanic or Latino, not Hispanic or Latino

These categorizations may be adjusted if the majority of the data lies in only 2 or 3 of the categories.

## 8.2 **Baseline Clinical Characteristics**

Baseline characteristics variables to be summarized will include ECOG performance status, Hormone Receptor and Human Epidermal Growth Factor Receptor Status at diagnosis, location of metastatic disease, FGF status, breast cancer stage at diagnosis, number of prior anticancer therapies, number of prior adjuvant anticancer therapies, number of prior neoadjuvant anticancer therapies, and number of prior metastatic anticancer therapies, and time since diagnosis. Categorizations are provided below:

- ECOG: 0, 1, 2
- HR/HER2 Status at Diagnosis: HER 2-positive, ER-positive (and not HER 2-positive), PR-positive (and not HER 2-positive and not ER-positive), Triple Negative (note the hierarchical nature of these four categories)
- FGF status: 11q, FGFR1, FGFR1 & 11q, Negative
- Breast cancer stage: Occult, 0, I, IIA, IIB, IIIA, IIIB, IIIC, IV
- Number of prior metastatic anticancer therapies: <3, 3-6, >6
- Location of metastatic disease: bone only, visceral only, bone and visceral
- Time since diagnosis (months):  $\leq 12, >12-24, >24;$

## 8.3 Medical History

Medical history data will be summarized using frequency tabulations by system organ class and preferred term.

## 9 STUDY DRUG EXPOSURE AND COMPLIANCE

The following analyses will be provided as a summary of study drug exposure and compliance:

- Duration of exposure (days): number of days from first dose of study drug to the last dose of study drug.
- Total study drug taken (mg): Number of milligrams of study drug taken during the study.
- Mean daily dose (mg): Total study drug taken / duration of exposure

The number of days on which drug was actually taken will also be summarized.

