9.2 Treatment Period

Before enrolling a patient, all eligibility criteria must be satisfied.

Patients will receive lucitanib 10 mg daily. Beginning on Day 1, lucitanib will be administered once daily to be swallowed with water (240 mL or 8 ounces). Patients should take lucitanib at approximately the same time each day, on an empty stomach, at least 2 hours before and 2 hours after a meal. Patients will record the dose and timing of administration of oral lucitanib in their daily dosing diary. Treatment with lucitanib is continuous but cycles will be defined as 28 days in duration.

BP self-monitoring should be completed at least twice a week by patients and measurements should be recorded in their diaries and brought to the clinic visits for review (see [Section 9.5.1.3](#)).

Unless otherwise specified, all patients will undergo the following procedures and assessments.

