9.5.5 PK Sub Study

Up to 20 patients will participate in the PK sub study. PK sampling will be performed at specified time points on each on the following two days:

- Day –7: lucitanib in tablet formulation
- Day 1: lucitanib in capsule formulation

The dose assigned for patients participating in the PK sub study will be the same for Days -7 and 1 and depends on the version of the amendment approved at the time of patient enrollment (Amendment #3: 15 mg; Amendment #4: 10 mg).

The total time from the Day -7 visit to the Cycle 1 Day 1 visit must not be fewer than 7 days, but may be greater than 7 days, if necessary. Lucitanib will not be taken between Day -7 and Cycle 1, Day 1.

PK specimens will be taken on Day -7 and Day 1 PK specimens will be collected 5–10 min pre-dose, and post-dose at 15 (± 2) min, 30 (± 3) min, 1 hr (± 5 min), 1.5 hr (± 5 min), 2.5 hr (± 10 min), 4 hr (± 15 min), 6 hr (± 15 min), 8 hr (± 15 min), 10 hr (± 30 min) (optional), and 24 hr (± 30 min). Refer to the Laboratory Manual for sample handling instructions.

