#### 12.2.3 Overall Survival (OS)

OS is defined as 1+ the number of days from the date of first dose of study drug to the date of death due to any cause. Patients without a documented date of death will be censored on the last date the patient was known to be alive.

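### SAP 9 counts the PK sub-study's mandated drug-free gap as exposure and leaves the day count ambiguous, so mean daily dose can misstate the dose taken

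*SAP*

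**What the plan says.** SAP section 9 defines three linked quantities. Duration of exposure is the "number of days from first dose of study drug to the last dose of study drug". Total study drug taken is the "Number of milligrams of study drug taken during the study". The ratio follows as "Mean daily dose (mg): Total study drug taken / duration of exposure". The section also summarises how many days a dose was taken, but does not use that count as the denominator. It has no rule for the PK sub-study and none for a patient with a single dose.

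Elsewhere the SAP writes its day count out. In section 12.1.1, "PFS is defined as 1+ the number of days from the date of first dose of study drug"; in section 12.2.3, "OS is defined as 1+ the number of days from the date of first dose of study drug".

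PK sub-study patients take one tablet dose on Day -7 and then start daily dosing on Cycle 1 Day 1 (C1D1). Protocol 5.1.1 and SAP 2.2.1 place their screening before Day -7 as the first dose of lucitanib. Protocol 9.5.5 requires at least 7 days between the two visits, sets no maximum, and states: "Lucitanib will not be taken between Day -7 and Cycle 1, Day 1". SAP 2.2.6 plans up to 20 such patients and allows more to be added.

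**The concern.** Mean daily dose should tell a reader how much drug patients took per day of intended dosing. SAP 9 can miss this in two ways.

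- **PK gap.** The clock starts on Day -7, so days on which the protocol forbids dosing enter the denominator. A patient who followed the protocol exactly looks under-dosed.
- **Day count.** If the count is last date minus first date, the denominator is one day short of the number of daily doses. A compliant patient then appears to take more than the dose given, and a patient with one dose has no defined value. The Safety Population (SAP 5) includes anyone with at least one dose, so that case can arise.

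At stake is the accuracy of one descriptive exposure table, mainly its patient-level values and extremes. SAP 4 presents summaries by starting dose. Under Protocol 9.5.5, PK sub-study patients may have started at 15 mg or 10 mg depending on the amendment, so the gap effect need not fall equally on the two columns.

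**Working it through.** The documents state no exposure figure, so there is none to reproduce. The check applies the SAP 9 formula to patients who miss no dose.

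**Inputs**
- D, the daily dose: 10 mg (Protocol 9.2: "Patients will receive lucitanib 10 mg daily"), or 15 mg for those enrolled under Amendment #3.
- n, the number of consecutive daily doses from C1D1: illustrative values. A cycle is 28 days.
- G, the days from Day -7 to C1D1: at least 7 (Protocol 9.5.5). G = 14 is illustrative, since no maximum is stated.

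**Step 1: PK sub-study patients.** Total dose is D(n + 1), including Day -7. Last date minus first date is G + n - 1; an inclusive count is G + n.

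| D | G | n | Last minus first | Inclusive |
|---|---|---|---|---|
| 10 | 7 | 14 | 150/20 = 7.50 | 150/21 = 7.14 |
| 10 | 7 | 28 | 290/34 = 8.53 | 290/35 = 8.29 |
| 10 | 7 | 56 | 570/62 = 9.19 | 570/63 = 9.05 |
| 10 | 7 | 112 | 1130/118 = 9.58 | 1130/119 = 9.50 |
| 10 | 14 | 28 | 290/41 = 7.07 | 290/42 = 6.90 |
| 15 | 7 | 28 | 435/34 = 12.79 | 435/35 = 12.43 |

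The ratio (n + 1)/(G + n - 1) is below 1 whenever G exceeds 2. Because G is at least 7, every fully compliant sub-study patient falls below the dose taken on dosing days, under either count.

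**Step 2: patients outside the sub-study.** Total dose is Dn and last minus first is n - 1, giving Dn/(n - 1). At 10 mg:

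| n | Last minus first | Excess | Inclusive |
|---|---|---|---|
| 1 | 10/0, undefined | n/a | 10.00 |
| 14 | 140/13 = 10.77 | 7.7% | 10.00 |
| 28 | 280/27 = 10.37 | 3.7% | 10.00 |
| 112 | 1120/111 = 10.09 | 0.9% | 10.00 |

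This part depends entirely on the count not being inclusive.

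**Step 3: effect on a group mean.** Suppose everyone takes 28 daily doses of 10 mg from C1D1, with G = 7 and 20 sub-study patients. On last minus first the mean is [(N - 20) × 10.37 + 20 × 8.53]/N, which is 9.91 for N = 80, 10.06 for N = 120 and 10.19 for N = 200. The two effects pull in opposite directions. On an inclusive count only the gap effect remains: for N = 80, (60 × 10.00 + 20 × 8.29)/80 = 9.57.

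**Step 4: test of the repair.** Adding one day alone leaves the sub-study patient at 290/35 = 8.29. Starting the denominator at C1D1 while keeping the Day -7 dose in the numerator overshoots: 290/28 = 10.36. Taking both from C1D1 with an inclusive count gives 280/28 = 10.00.

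**The case against.** The strongest reply is that SAP 9 gives no subtraction formula, and its wording can be programmed inclusively. The added day in PFS and OS supports the other reading but does not prove it. The SAP also omits the added day for duration of response (section 12.2.1), so its absence in section 9 may be loose drafting. This stands: the above-dose values and the zero denominator are conditional. It does not help with the PK gap, where an inclusive count lowers the value further.

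A second reply is that a calendar average from first to last dose is what SAP 9 defines, and for sub-study patients that average is arithmetically correct. This also stands, as far as it goes. But the gap is imposed by the design, and in a section on exposure and compliance the figure would mislead without a rule or footnote.

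Two stronger inferences are tempting. A reader might take mean daily dose to be the SAP's measure of whether 10 mg can be sustained where 15 mg could not. Neither document says so: SAP 9 attaches no threshold, comparison or decision to it. A reader might also infer that sub-study patients would be recorded as dose-reduced. The plan does not derive reductions from mean daily dose: Protocol 11.2.5.1 counts reductions and interruptions directly, and SAP 17.1 tabulates adverse events leading to them. The count of days with a dose taken in SAP 9 would also help show the undosed days.

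**Conclusion.** The PK gap point holds under either day count. With the minimum 7-day gap, a fully compliant 10 mg sub-study patient shows 8.53 mg/day through Cycle 1 (8.29 inclusive) and 9.58 at 112 days (9.50 inclusive). A longer gap lowers these values. It concerns up to about 20 patients, unless more are added.

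The day-count point is conditional. By the SAP's own PFS and OS convention, compliant patients outside the sub-study exceed the dose given by 3.7% at 28 doses and 0.9% at 112, and a one-dose patient is undefined. An inclusive reading removes all of this. The supportable statement is that SAP 9 does not settle the count, not that it certainly drops a day.

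The figures assume no missed doses, a constant dose, and illustrative exposure lengths; any gap above 7 days is likewise assumed. The consequence is confined to a descriptive summary. No efficacy result, sample-size figure or decision criterion changes. This is a minor clarification worth making.

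**What to change.** In SAP 9:

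1. Define duration of exposure as last dose date minus first dose date plus 1.
2. For PK sub-study patients, compute both the total dose and the duration used in mean daily dose from C1D1. This takes the Day -7 dose out of the numerator as well as the gap out of the denominator.
3. Report the Day -7 dose separately. For a patient who received only that dose, state that mean daily dose is not calculated and list the patient.

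Compliant patients then show exactly 10.00 or 15.00 mg/day at any exposure length, including a single dose outside the sub-study.

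The cost is a few lines in one SAP section, before database lock. The diary already records the date and dose of each administration (Protocol 9.5.9), so no new data are needed.
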